#### 10.1.4 Severity

The investigator will evaluate all AEs with respect to both seriousness (results in outcomes as above) and **severity** (intensity or grade). AEs will be graded for severity according to the *DAIDS Table for Grading the Severity of Adult and Pediatric Adverse Events*, (also known as the DAIDS AE Grading Table; see [Appendix D](#) for the URL).

For specific events that are not included in the DAIDS AE Grading Table, the generic scale below is to be used:

**TABLE 3. GENERIC AE GRADING SCALE**

Grade 1	Symptoms causing no or minimal interference with usual social and functional activities
Grade 2	Symptoms causing greater than minimal interference with usual social and functional activities
Grade 3	Symptoms causing inability to perform usual social and functional activities
Grade 4	Symptoms causing inability to perform basic self-care functions, or medical or operative intervention indicated to prevent permanent impairment, persistent disability, or death
Grade 5	Events resulting in death

### 10.1.5 Causality

Causality refers to the likelihood that the event is related to the study intervention. It will be assessed for SAEs and UPs. This assessment will be made for both the agent under investigation (hIVIG) and the study-provided background therapy of remdesivir using the following guidelines:

- Reasonable possibility – There is a clear temporal relationship between the study intervention and the event onset, and the AE is known to occur with the study intervention or there is a reasonable possibility that the study intervention caused the AE. Reasonable possibility means that there is evidence to suggest a causal relationship between the study intervention and the AE.
- No reasonable possibility – There is no evidence suggesting that the study intervention caused the event, there is no temporal relationship between the study intervention and event onset, or an alternate etiology has been established.

The causality assessment is based on available information at the time of the assessment of the event. The investigator may revise these assessments as additional information becomes available.

### 10.1.6 Expectedness

Expectedness will be assessed for SAEs using the Reference Safety Information section of the IBs for the hIVIG and remdesivir.

The expectedness assessment is based on available information at the time of the assessment of the event. The investigator may revise these assessments as additional information becomes available.

## **10.2 Schedule for Data Collection and Reporting of Specific Events**

### **10.2.1 Infusion-related reactions**

Infusion related signs/symptoms of any grade that are new or have increased in grade compared to their pre-infusion level are reported for the hVIG/placebo if they occur during or within 2 hours post infusion. Any infusion related reaction assessed as meeting SAE criteria will be reported as an SAE. Similarly, any grade 3 or 4 infusion related reaction will be reported as an AE.

### **10.2.2 Targeted Laboratory abnormalities**

Selected laboratory tests are performed prior to infusion and on Day 7. These values are associated with a severity grade centrally using the laboratory test results reported on the eCRFs with normal ranges, and with the DAIDS AE Grading Table.

Other laboratory abnormalities identified in the course of the participant's clinical care are not reported as AEs (e.g., an isolated elevated glucose level) unless they are associated with a specific clinical diagnosis/syndrome, in which case they are reported if they meet the reporting criteria of one of the other safety outcomes. In addition, if an isolated laboratory test result meets SAE reporting criteria (e.g., a serious event related to the study intervention), it should be reported as an SAE.

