### *Other Reactions*

- Renal dysfunction, acute renal failure, and osmotic nephropathy may occur with immune globulin intravenous products in predisposed patients. Renal dysfunction and acute failure occur more commonly in patients receiving IVIG products containing sucrose. The hIVIG products in this study do not contain sucrose.
- Transfusion-related acute lung injury (TRALI), although very rare, may occur and is characterized by severe respiratory distress, pulmonary edema, hypoxemia, normal left ventricular function, and fever.
- The infused volumes of study product may be as high as 200 mL, so there is the risk of volume overload in the recipient which could cause pulmonary edema. Transfusion-associated circulatory overload (TACO) has been associated with plasma infusion and may be clinically indistinguishable from TRALI even though the physiologic mechanisms differ. TACO is hydrostatic, not permeability, edema and more responsive to diuresis when it occurs. Patients with pre-existing conditions who may not tolerate the volume of hIVIG/placebo to be given will be excluded from this study, but this condition could still occur in recipients.
- There are case reports of pulmonary emboli occurring after administration of IVIG and plasma therapy, though definitive studies assessing risk are lacking. Pulmonary emboli have been shown to develop in approximately 10-15% of critically ill adults. Other thrombotic events, including myocardial infarction, cerebral vascular accident, and deep vein thrombosis may also occur.

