#### **8.2.5 Dose Modification**

If the estimated glomerular filtration rate (eGFR) decreases to < 25 mL/min, the remdesivir infusion should not be given on that day. The infusion may be resumed on the next day if the eGFR returns to  $\geq$  30 mL/min. If the participant's renal function worsens to the point that they require hemodialysis or hemofiltration, remdesivir will be discontinued.

If the ALT and/or AST increases to > than 5 times the upper limit of normal, the dose of remdesivir should be withheld and not be restarted until the ALT and AST reduces to  $\leq$  5 times the upper limit of normal.

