### 9.1.2 Follow-up assessments

Participants will be followed through Day 28 following randomization for collection of study data. Clinical data targeted to components of the primary and secondary endpoints will be collected daily during hospitalization, and at scheduled visits to day 28 after discharge. This will include discharge status, development of key medical conditions, vital signs including SpO2. On Day 7, interim targeted physical exam and concomitant medications will be collected along with the results of blood tests for serum creatinine, ALT or AST, white blood cell count, hemoglobin, platelets, lymphocytes, and C-reactive protein (CRP).

AEs of any grade severity will be collected on Day 0 prior to infusion and on Days 1, 3, 7, and 28 (AEs present on those days). Incident AEs of grade 3 or 4 severity will be collected through Day 7 and all SAEs will be collected through Day 28.

The primary ordinal outcome measure will be assessed daily while the participant is hospitalized and on Day 3, 5, Day 7 (primary endpoint), Day 14 and Day 28 for all participants. Items necessary for determination of NEWS will be collected on Day 3. The Borg dyspnea score will be evaluated at baseline and day 7.

For participants who are no longer hospitalized, in-person visits will be done on study days where blood is collected (Days 1, 2, 3, 7, and 28). For other visits (Day 5 and Day 14), contact with the participant for the purpose of study data collection may be performed by telephone, recognizing that certain components of the endpoints (e.g. SpO2) are not likely available from outpatients. Other information as possible will be gathered.

On Days 1, 2, 3, 7, and 28, plasma and serum samples (four 1 mL aliquots of both plasma and serum at each visit) will be obtained for central testing of antibody levels (including neutralizing antibodies) to SARS-CoV-2 and for storage for future related research. Two 9 mL tubes, SST and EDTA, of blood (18 mL total) will be drawn in order obtain the 8 aliquots.

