## 10 SAFETY REPORTING

The safety evaluation of the study intervention includes several components, all of which will be regularly reviewed by the independent DSMB. For this protocol, the term “study intervention” refers to the hIVIG/placebo and to remdesivir.

With the exception of infusion related reactions of any grade, which are only collected for the hIVIG/placebo, all other AEs are collected for the study intervention (either the hIVIG/placebo or study-provided SOC treatment). Selected events will be reported to regulators and IRBs/ethics committees in addition to being regularly reviewed by the DSMB.

The following information will be collected to evaluate safety:

- Infusion-related reactions of any grade severity during and within 2 hours post-infusion of the hIVIG/placebo.
- Clinical AEs of any grade severity will be collected on Days 0, 1, 3, 7, and 28 (AEs present on those days).
- Targeted laboratory abnormalities of any grade severity at Day 7.
- Incident grade 3 and 4 clinical adverse events occurring through Day 7 (isolated laboratory abnormalities that are not associated with signs or symptoms are not recorded).
- Clinical events that are collected as part of the primary ordinal outcome or as secondary outcomes through Day 28. These are protocol exempt events and are not reported as SAEs unless they are considered as related to the study intervention.
- Serious adverse events, including laboratory-only serious events, considered related to the study intervention (either the hIVIG/placebo or a study-provided SOC treatment) through Day 28.
- Serious adverse events that are not collected as part of the primary ordinal outcome or as a secondary outcome through Day 28.
- Unanticipated problems through Day 28.
- Deaths through Day 28.

An overview of safety data collected during the study is given in Table 2.

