### **10.2.4 Incident Grade 3 and 4 clinical adverse events through Day 7**

From the time of randomization on Day 0 through Day 7, clinical events reaching Grade 3 or 4 severity level will be reported as AEs unless they are a protocol-specified exempt event (see below).

Any medical condition of grade 1 and 2 that is present at Day 0 will be reported as an AE if it increases to Grade 3 or 4 by Day 7.

Isolated laboratory abnormalities will not be recorded on the eCRF for grade 3 and 4 events. However, as noted above, if an isolated laboratory result meets SAE criteria, it should be reported as an SAE.

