  - A composite of SAEs and death through Day 28 (including and excluding exempt events and each component separately analyzed)
  - Prevalence of clinical AEs of any grade on Days 0, 1, 3, 7, and 28; AEs will be summarized by grade and day, and by MedDRA® system organ class and grade. (AEs present on those days).
  - Summaries of UPs and SUSARS, and listings of SAEs, UPs, SUSARs and deaths.
  - Change in laboratory test values from baseline to Day 7, and incidence of grade 3 and 4 laboratory abnormalities at Day 7.

AEs will be coded with MedDRA, version 23.1. In addition to the tables, listing of participants with grade 3 or 4 events, SAEs or deaths will be provided with the MedDRA preferred term (PT) and study day of AE.

Further safety assessments may be considered including by study product/matching placebo group (see Section 7.5).

Because the infusion volume in this protocol is significant (250 mL for remdesivir and up to 400 mL for hVIG/placebo), as a guideline, the DSMB will be asked to consider halting enrollment if more than 5% of participants experience a grade 3 or 4 infusion AE or if more than 10% do not complete the infusion due to an AE(s). This will be informed by the lower bound of the 95% confidence interval which will not be adjusted for multiplicity. When this occurs, differences will be compared by randomized group. If the study is temporarily halted or stopped for safety reasons, institutional review boards/ethics committees will be informed.

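### Creatinine is compared only at Day 7 and at face value, so transient laboratory-only kidney injury is missed and a participant on renal replacement can look normal in that table

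*Protocol*

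**What the plan says.** **The risk.** Protocol 3.1.2, under Other Reactions: "Renal dysfunction, acute renal failure, and osmotic nephropathy may occur with immune globulin intravenous products in predisposed patients". The same paragraph says such injury is more common with sucrose-containing products and that the trial products contain none. Section 3.1.2 also lists hemolysis among rare serious reactions.

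**The measurement.** Protocol 10.2.2: "Selected laboratory tests are performed prior to infusion and on Day 7". Protocol 9.1.2, on Day 7: "concomitant medications will be collected along with the results of blood tests for serum creatinine", with hemoglobin in the same list. Appendix B marks local laboratory testing at screening and Day 7 only.

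**What is not recorded.** Protocol section 10, on incident grade 3 and 4 events: "isolated laboratory abnormalities that are not associated with signs or symptoms are not recorded". Section 10.2.4 repeats it: "Isolated laboratory abnormalities will not be recorded on the eCRF for grade 3 and 4 events". Section 10.2.2 keeps other laboratory abnormalities found in care out of AE reporting "unless they are associated with a specific clinical diagnosis/syndrome, in which case they are reported if they meet the reporting criteria" of another safety outcome. Sections 10.2.2 and 10.2.4 both add that an isolated result meeting SAE criteria is reported as an SAE.

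**The analysis.** SAP 7.2 lists, among the other safety outcomes: "Change in laboratory test values from baseline to Day 7, and incidence of grade 3 and 4 laboratory abnormalities at Day 7". Neither document says how a creatinine drawn during renal replacement is graded or analysed.

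**Dialysis.** It is an organ-dysfunction outcome through Day 28 (Protocol 4.2), a systematically collected exempt event (10.2.5) and part of category 6 of the ordinal outcome (Appendix F).

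**Monitoring in care.** Protocol 8.2.4 calls for renal function to be monitored during remdesivir, and 8.2.5 ties dosing to it: "If the estimated glomerular filtration rate (eGFR) decreases to < 25 mL/min, the remdesivir infusion should not be given on that day".

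**The concern.** There is one infusion, on Day 0, and one protocol creatinine after it, a week later. A rise that comes and goes in between leaves no trace in the laboratory data. If the rise is not serious and no clinician records a diagnosis, no other form picks it up either.

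The second problem concerns direction. Renal replacement lowers serum creatinine. A participant who is dialysed because the kidneys have failed may have a Day 7 value at or below baseline. Taken at face value, the worst renal outcome then pulls the mean change towards benefit and adds nothing to the grade 3 or 4 count. This is the only laboratory comparison of renal safety in SAP 7.2. If hIVIG did cause kidney injury, that table could understate it.

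People at higher risk are in the trial: SAP 1.2.3 reports renal impairment in 7% at baseline (0.07 × 593 ≈ 42 participants).

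**Working it through.** The plan gives no figure on this point to reproduce. The check is which renal events reach which dataset, followed by the timing of the Day 7 sample.

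**Step 1. Routes of capture.**

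| Renal event between infusion and Day 7 | Captured by |
|---|---|
| New dialysis | Organ-dysfunction outcome, exempt-event eCRF, category 6 while on it |
| Grade 3 or 4 clinical event | Collected on any day through Day 7 (10.2.4) |
| Laboratory abnormality with a clinical diagnosis | Reported if it meets another safety outcome's criteria (10.2.2) |
| Laboratory result meeting SAE criteria | SAE report (10.2.2, 10.2.4) |
| Lower-grade clinical AE | Any-grade collection on Days 1, 3, 7 and 28 (10.2.3) |
| Non-serious rise, no diagnosis, still present on Day 7 | Day 7 creatinine |
| Non-serious rise, no diagnosis, settled before Day 7 | Nothing |

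The any-grade collection does not rescue the last row, because 10.2.3 describes AEs that the participant reports that day, and a symptomless creatinine rise cannot be self-reported.

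**Step 2. What the Day 7 sample can see.** Let an episode start on day *o* and last *d* days, so that it covers days *o* to *o + d − 1*. The sample catches it only if *o + d − 1* ≥ 7. The documents give neither onset nor duration, so both are assumptions here. With onset equally likely on Days 1 to 7, the share caught is *d*/7.

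| Duration (days) | Day 7 creatinine | Days 1, 3, 7 AE collection, if recognised as a clinical AE |
|---|---|---|
| 1 | 1/7 = 14% | 3/7 = 43% |
| 2 | 2/7 = 29% | 5/7 = 71% |
| 3 | 3/7 = 43% | 6/7 = 86% |
| 5 | 5/7 = 71% | 7/7 = 100% |

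For onset on Days 1 to 3, the latest last day of a four-day episode is 3 + 4 − 1 = 6. The Day 7 sample therefore catches no episode of four days or less. At five days it catches only onset on Day 3 (1/3).

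**Step 3. Creatinine during renal replacement.** Protocol 10.2.2 says severity grades are assigned centrally from the reported laboratory results. SAP 7.2 then uses those grades and the change from baseline. Nothing in either step carries the dialysis record into the laboratory table, so a lowered value is analysed as measured.

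**Step 4. A ceiling on how many.** Anyone alive and on renal replacement on Day 7 is in category 6. The design assumes 6.3% (placebo) and 4.0% (hIVIG) in category 6 on Day 7 (Table 1). With 579/2 ≈ 290 per arm, that is at most 0.063 × 290 ≈ 18 and 0.040 × 290 ≈ 12 participants. Category 6 also covers invasive ventilation, ECMO, mechanical circulatory support and vasopressors, so these are upper limits under the design assumptions, not estimates.

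**The case against.** The strongest reply is that renal injury does not rest on one blood sample. Step 1 shows several other routes, and a dialysed participant is in category 6 of the primary outcome, so cannot pass as well in the trial overall. That stands. A reader might infer that all renal injury resolving before Day 7 goes unrecorded, or that dialysis is hidden. The documents support neither.

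A reader might also attach a power loss. With 290 per arm and assumed true rates of 5% and 10%, two-sided 0.05, power is 63% on the peak value and 35% if half the cases have resolved by Day 7 (2.5% against 5%). The arithmetic is sound, but the rates and the resolved share come from no document, and the calculation treats every resolved case as lost, ignoring the other routes. It does not measure the gap.

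Three further points have weight. Leaving isolated laboratory values out of the grade 3 and 4 events is a stated design choice. The protocol cites the DAIDS grading table without reproducing it, so whether that table treats dialysis separately cannot be checked here. And sections 8.2.4 and 8.2.5 do not require daily tests, so it is an inference that the intermediate values exist.

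These points narrow the concern without removing it. Recording dialysis elsewhere does not correct the creatinine table. As an exempt event, dialysis is not reported as a grade 3 or 4 AE, nor as an SAE unless judged related (Protocol 10.2.5). SAP 7.2 lists a composite without exempt events as a further analysis, which suggests that the primary safety composite includes them. It does not say so outright, and a sentence confirming it would help.

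**Conclusion.** The concern holds in a limited form. Laboratory-defined kidney injury short of dialysis is measured only by the baseline and Day 7 creatinine, and a non-serious, undiagnosed rise that resolves sooner is not captured. In addition, SAP 7.2 has no rule for creatinine under renal replacement, so its one laboratory renal comparison can understate harm.

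The size cannot be stated from the documents: they give no rate, timing or duration of renal injury and no count of participants on renal replacement. The timing shares in the working rest on assumed uniform onset and fixed duration. The primary efficacy result is not affected. The point is worth correcting because the risk is named and the main correction uses data already collected.

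**What to change.** **In SAP 7.2, before unblinding:**

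1. Count any participant with new-onset renal replacement between infusion and Day 7 as the highest creatinine grade, whatever the measured value. Restrict this to participants not on it at baseline: the listed exclusions do not name chronic dialysis, so established dialysis could otherwise be scored as incident.
2. Report by arm the combined incidence of grade 3 or 4 creatinine or new renal replacement.
3. Show mean creatinine change with and without these participants, and state how many were set aside per arm. Both versions are needed, because removing them drops the worst cases on a post-randomisation event.

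The cost is SAP wording and programming; no new data are needed.

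**Optional, where feasible:** abstract the highest creatinine and lowest hemoglobin from routine care between infusion and Day 7, and report them as a supplementary worst-value summary beside the Day 7 analysis. Enrollment is complete, so this means retrospective chart work at up to 63 sites in 11 countries. It also carries a sampling bias. Inpatients are tested more often than discharged participants, and Protocol 5.5.3 works with 45% to 58% discharged by Day 7. The Day 7 analysis should therefore stay in place.

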### **10.2.3 Clinical adverse events of any grade severity on Days 0, 1, 3, 7 and 28**

On Day 0 prior to infusion and on Days 1, 3, 7 and 28 the prevalence of AEs of any grade severity that the participant reports that day will be collected. This information supplements the information on grade 3 and 4 events through Day 7 that is collected.

### **10.2.4 Incident Grade 3 and 4 clinical adverse events through Day 7**

From the time of randomization on Day 0 through Day 7, clinical events reaching Grade 3 or 4 severity level will be reported as AEs unless they are a protocol-specified exempt event (see below).

Any medical condition of grade 1 and 2 that is present at Day 0 will be reported as an AE if it increases to Grade 3 or 4 by Day 7.

Isolated laboratory abnormalities will not be recorded on the eCRF for grade 3 and 4 events. However, as noted above, if an isolated laboratory result meets SAE criteria, it should be reported as an SAE.

### 10.2.5 Protocol-specified exempt events

These events are listed in sections 4.1 and 4.2 and are collected systematically during study follow-up on eCRFs. These events will not be reported as Grade 3 or 4 AEs even if they occur at that severity grade. They also will not be reported as SAEs, even if they meet one or more of the criteria for seriousness, ***unless the investigator considered that there was a reasonable possibility that the study intervention caused the event.*** These events may occur during the initial hospitalization, lead to a re-admission, or occur in a later hospitalization during follow-up.

The following are **protocol-specified exempt events**:

- Death
- Stroke
- Meningitis
- Encephalitis
- Myelitis
- Myocardial infarction
- Myocarditis
- Pericarditis
- New onset of worsening of CHF (NYHA class 3 or 4)
- Arterial or deep venous thromboembolic events
- Respiratory failure defined as receipt of high flow nasal oxygen, noninvasive ventilation, or invasive ventilation
- Hypotension requiring vasopressor therapy
- Renal dysfunction requiring renal replacement therapy
- Hepatic decompensation
- Acute delirium
- Disseminated intravascular coagulation
- Microbiologically-proven severe infection (not including SARS-CoV-2)

### 10.2.6 Reportable SAEs

Reportable SAEs for this study are:

- Serious clinical AEs not reported as a study endpoint; and
- Any serious AE related to the study intervention

Deaths, life-threatening events, and others SAEs considered related to the investigational agent, irrespective of whether the event is mentioned above as a protocol-specified exempt event, that occur from the time of infusion of the hVIG/placebo begins through the Day 28 visit must be reported by sites on the SAE eCRF to the sponsor via the INSIGHT Safety Office. These events must be reported **within 24 hours of site awareness**. All other SAEs must be reported within 3 days of site awareness.

SAEs are followed until the outcome of the SAE is known. If the outcome of an SAE is still unknown at the time of the final follow-up visit (Day 28), the outcome will be entered in the database as “unknown.”

Suspected unexpected serious adverse reactions (SUSARs) are SAEs that are assessed as related to a study-provided treatment and are unexpected per the Reference Safety Information of the IB for that treatment. SUSARs are reported from the INSIGHT Safety Office to applicable regulators in an expedited fashion. SUSARs that result in death or are immediately life-threatening are reported to regulators within 7 calendar days of receipt. All other SUSARs are reported to regulators within 15 calendar days. The INSIGHT Safety Office will generate a Safety Report for each SUSAR for distribution to investigators and other parties. Investigators are responsible for submitting Safety Report summaries that are received from the sponsor to their overseeing IRB/EC. Investigators must also comply with all reporting requirements of their overseeing IRB/EC.

Safety reports for SUSARs indicate the study intervention (i.e., are unblinded).

SAEs that are not protocol-specified exempt events and that are not related to the study intervention (investigational agent or treatment provided as SOC) must be reported on the SAE eCRF within 3 days of site awareness.

